A formal statistical justification of the sample size is not made. The sample size of approximately 30 subjects is planned. Every effort will be made to achieve at least 5 evaluable subjects per age cohort: 1 to < 12 years of age and 12 to < 18 years of age. The sponsor reserves the right to stop enrollment if the cohort requirements are not achieved.

Safety

All AEs will be listed by subject and by age cohort. The incidence of the following AEs will be summarized by system organ class and preferred term for overall subjects and by subjects in each age cohort: overall, serious, related to study drug and leading to the permanent discontinuation of study drug.

Vital signs will be listed and summarized. Laboratory test values will be presented in shift tables and by individual listings with flagging of values outside the normal reference ranges. ECG findings will be presented by listings and frequency tables, as appropriate.

The incidence of treatment emergent AEs will also be summarized by relationship to study drug and severity for all subjects and by subjects in each age cohort.

Efficacy

Per each diagnosis (IA or IM) accrued, the crude all-cause mortality rates will be calculated by dividing the number of deaths by the number of subjects in the full analysis set (FAS) (i.e., all enrolled subjects who received at least one dose of study drug), and a 2-sided exact 95% CI will be calculated. Each subject will be classified as either death or alive. Subjects who died on or before day 42/day 84/EOT, as well as subjects who are lost to follow-up before day 42/day 84/EOT will be counted as deaths.

Efficacy (*continued*)

Crude success rates and 2-sided exact 95% CIs will be calculated for the overall, clinical, radiological and mycological response at day 42, day 84 and EOT in the FAS.

For each efficacy endpoint, a summary will be presented for overall subjects and by subjects in each age cohort.

Pharmacokinetics

Observed plasma concentration data for isavuconazole will be presented in listings.

In addition, pharmacokinetic plasma concentrations will be analyzed using population pharmacokinetic model. Details of the model and modeling procedure will be provided in separate modeling report.

Pharmacodynamics

Not applicable.

Interim Analyses

Not applicable.

[figure not shown]
Data and Safety Monitoring Board and Adjudication Committees

A Data and Safety Monitoring Board will be utilized to monitor subject safety throughout the study.

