1.1 Background

As in adults, fungal infections remain an important cause of morbidity and mortality in pediatric subjects. In immunocompromised pediatric subjects, invasive mould infections (IMIs) are a leading cause of mortality [Georgiadou et al, 2012; Al-Rezqi et al, 2009; Burgos et al, 2008; Walsh et al, 2008; Sung & Johnston, 2007; Zaoutis et al, 2006]. In a large prospective multinational study to evaluate the epidemiology and spectrum of IMIs in children, which enrolled 131 pediatric subjects with proven or probable IMIs, the most common diagnosis was IA (75%), followed by other IMIs (17%) and IM (13%) [Wattier et al, 2015]. A large proportion of these subjects had some underlying immunosuppression. Overall mortality was 30% at 12 weeks [Wattier et al, 2015]. Another study identified 48 pediatric subjects with proven or probable IMIs from a retrospective single-center in the US [Georgiadou et al, 2012] and found similar trends with *Aspergillus* species being the most common organism and the majority of subjects being immunocompromised with hematologic malignancy and/or neutropenia. Overall mortality in this study was 31% at 12 weeks; in all subjects, death was attributed to both IMI and the underlying disease.

Invasive Aspergillosis: Risk factors and underlying disease characteristics for IA are comparable between adults and children with the most common being malignancy, such as acute myeloid leukemia (AML) and allogeneic hematopoietic stem cell transplant (HSCT). Chronic granulomatous disease, which is typically diagnosed in children, is also a risk factor [Dornbusch et al, 2009]. The Infectious Diseases Society of America guidelines for the treatment of IA do not distinguish between the disease characteristics in adults and children [Walsh et al, 2008]. Therefore, aside from systemic dosing differences, the treatment guidelines for these 2 populations do not differ.

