1.2 Nonclinical and Clinical Data

An overview of the nonclinical and adult clinical data of isavuconazole can be found in the latest version of the investigator's brochure (IB).

Isavuconazole has been investigated in a phase 1 pharmacokinetic, safety and tolerability study in pediatric subjects following intravenous administration. In this study, a total of 27 pediatric subjects received at least 1 dose of study drug (Protocol 9766-CL-0046). Nine subjects were between 1 and < 6 years of age, 8 subjects were between 6 and < 12 years of age and 10 subjects were between 12 and < 18 years of age. A majority of subjects were white and male. Most subjects had an underlying malignancy. Subjects weighing \leq 40 kg received 10 mg/kg of isavuconazonium sulfate, and subjects > 40 kg received 372 of isavuconazonium sulfate intravenously daily, after a loading regimen.

The vast majority of subjects experienced at least 1 adverse event (AE), and serious adverse events (SAEs) were experienced by about half of all subjects, which is expected given the medical history of the subjects enrolled. About a third of subjects experienced drug-related AEs. Important drug-related events included gastrointestinal (GI) disorders and infusion-related reactions. Two subjects were withdrawn from the study due to an AE. The events leading to withdrawal were increased liver enzymes and QT prolongation, and both events were considered related to study drug. No differences were observed in the AE experience between the 3 age cohorts.

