3.3 Exclusion Criteria

Subject will be excluded from participation if any of the following apply:

1. Subject has familial short QT syndrome, is receiving medications that are known to shorten the QT interval, or has a clinically significant abnormal ECG.
2. Subject has evidence of hepatic dysfunction defined as any of the following:
 - Total bilirubin (TBL) ≥ 3 times the upper limit of normal (ULN)
 - Alanine transaminase (ALT) or aspartate transaminase (AST) ≥ 5 times the ULN
 - Known cirrhosis or chronic hepatic failure

3. Subject has used strong cytochrome P450 (CYP3A4) inhibitors or inducers such as ketoconazole, high dose ritonavir, rifampin/rifampicin, long acting barbiturates (e.g., phenytoin), carbamazepine and St. John's Wort in the 5 days prior to the first dose of study drug.
4. Subject has another IFI other than possible, probable or proven IA or IM.
5. Subject has chronic aspergillosis, aspergilloma or allergic bronchopulmonary aspergillosis.
6. Subject has received mould active systemic antifungal therapy, effective against the primary IMI, for more than 4 days during the 7 days preceding the first dose.

Note: Prior use of prophylactic antifungal therapy is acceptable. In case of breakthrough IA while on prophylactic mould-active azole class drugs, additional documentation will be required to be submitted to the sponsor medical monitor or designee to approve subject enrollment.

7. Subject has known history of allergy, hypersensitivity or any serious reaction to any of the azole class antifungals, or any components of the study drug formulation.
8. Subject has any condition, which, in the investigator's opinion, makes the subject unsuitable for study participation.
9. Subject is unlikely to survive 30 days in the investigator's opinion.
10. Subject has received investigational drug, with the exception of oncology drug trials, or trials with investigational drugs treating graft versus host disease, within 28 days or 5 half-lives, whichever is longer, prior to screening.

Waivers to the exclusion criteria will **NOT** be allowed.

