5.3 Efficacy and Pharmacokinetic Assessments

5.3.1 Efficacy Assessment

All clinical, mycological, radiological assessments and diagnostic tests performed to document the baseline mould infection must be recorded. Criteria for possible, probable and proven disease based on the EORTC/MSG criteria require evidence including host factors (neutropenia, hematological malignancy, etc.), mycological criteria (positive culture from normally sterile site, BAL fluid, serum or BAL GM and histology of tissue demonstrating the

presence of fungal elements), and clinical signs and symptoms (radiological evidence of fungal disease at the infected body site). These data will be recorded in the eCRF.

During treatment with study drug, record any tests performed to demonstrate changes from baseline or evaluate the status of the fungal infection, such as mycological evidence of fungal culture or histology results (positive and negative) from the relevant site of infection or any new site, new fungal infection, changes in clinical signs and symptoms, including radiological findings relevant to the baseline fungal infection under treatment, and any serological markers performed (serum GM) and any surgical procedures. Record any procedures conducted to further assess or treat the fungal infection such as surgical debridement, amputation, etc. and the results of such procedures. Negative results of tests demonstrating resolution of infection should also be documented and recorded in the eCRF. Mortality status will be assessed per [Table 1 and Table 2 Schedule of Assessments].

Every effort should be made to speciate and characterize any fungal organisms grown in cultures. Results of susceptibility testing done locally will be collected. Fungal isolates from all positive fungal cultures should be stored and a reference laboratory will be made available by the sponsor. The reference laboratory will provide confirmation of the fungal genus and species, as well as in vitro susceptibility to isavuconazole, as well as relevant mould-active antifungal drugs. The reference laboratory results will not be available until after the end of the study.

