7.5.2 Laboratory Assessments

For quantitative laboratory measurements descriptive statistics will be used to summarize results and change from baseline for subjects in the SAF by treatment visit.

Shifts relative to normal ranges from baseline to each time point during treatment period in lab tests will also be tabulated. Laboratory data will be displayed in listings.

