6.5.2 Clinical Laboratory Evaluation

Clinical laboratory samples will be collected and reported based on timepoints as listed in the Protocol Table 1 and Table 2 in Section 1 based on lab sample collection visits.

Clinical Laboratory variables will be created for each of the following:

| Chemistry: | Hematology: |
|--|--|
| Sodium | Red blood cells |
| Potassium | White blood cells (total leukocytes) |
| Magnesium | Hemoglobin |
| Calcium | Hematocrit |
| Chloride | Platelets (thrombocytes) |
| Glucose | Neutrophils (ANC) |
| Creatinine | Eosinophils |
| Creatine phosphokinase/Creatine kinase | Basophils |
| Alkaline phosphatase (ALP) | Lymphocytes |
| | Monocytes |
| | Blast cells |
| Hepatic Panel: | Pregnancy Test: |
| Albumin | Human chorionic gonadotropin (hCG) |
| Total bilirubin (TBL) | |
| Direct Bilirubin | |
| Total Protein | |
| Alanine aminotransferase (ALT) | |
| Aspartate aminotransferase (AST) | |
| | Other: |
| | Serum galactomannan (GM) |
| | Partial thromboplastin time/international normalized ratio (PTT/INR) |

The baseline value will be the last non-missing value taken on or prior to first dose of study drug. Quantitative values evaluated by the central laboratory including hematology and biochemistry will be summarized using mean, standard deviation, minimum, maximum and median at each analysis visit. Additionally, a within-subject change will be calculated as the post-baseline measurement minus the baseline measurement and summarized in the same

way. Clinical Laboratory data will be reported using the SAF population by Clinical Laboratory Tests collected at baseline and days 7, 28, 56 and 84 (or EOT).

Shifts relative to normal ranges from baseline to each time point during treatment period in lab tests will also be tabulated. Laboratory data will be displayed in listings. For quantitative laboratory measurements descriptive statistics will be used to summarize results and change from baseline for subjects.

Each laboratory result will be classified as low, normal, or high at each visit according to the laboratory supplied reference ranges as specified in the Protocol.

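### Outside the liver table, the low/normal/high shift tables cannot count the children who worsen from an already abnormal baseline; this matters most for blood counts

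*Protocol*

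**What the plan says.** Protocol 7.5.2 plans descriptive statistics of values and change from baseline by visit, and adds: "Shifts relative to normal ranges from baseline to each time point during treatment period in lab tests will also be tabulated". SAP 6.5.2 supplies the categories: "Each laboratory result will be classified as low, normal, or high at each visit according to the laboratory supplied reference ranges". The Protocol synopsis (Statistical Methods, Safety) repeats the plan: "Laboratory test values will be presented in shift tables and by individual listings with flagging of values outside the normal reference ranges".

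Neither document names a grading scale for laboratory values. Neither plans a shift to the worst on-treatment value. The liver table in SAP 6.5.3 is the one place with graded limits: it takes each child's highest value and counts ALT above 3, 5, 10 and 20 times the upper limit, with bilirubin and combined criteria, ignoring baseline.

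On the population, Protocol 5.3.1 lists among the diagnostic evidence "host factors (neutropenia, hematological malignancy, etc". Protocol 3.3 sets numerical laboratory limits only for bilirubin and transaminases.

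**The concern.** A three-level shift can show worsening only in a child who starts in range or on the opposite side of it. The trial recruits from a population in which low counts at entry are plausible. In a cited pediatric cohort, Protocol 1.1 describes "the majority of subjects being immunocompromised with hematologic malignancy and/or neutropenia", and of the drug's earlier pediatric study Protocol 1.2 says "Most subjects had an underlying malignancy".

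Safety is the first objective listed (Protocol 2.1.1) and laboratory parameters are a named safety endpoint (2.3.1). With no comparator and about 30 children, the number who deteriorated from their own baseline is among the few laboratory results a reader can interpret. For blood counts, the shift table may leave out the children with the least reserve, while a trivial crossing of the limit in another child is counted.

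**Working it through.** The plan gives no figure on this point, so there is none to reproduce.

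**Step 1: the classification rule.** Let L be the lower reference limit, b the baseline value and v a later value. If b < L, every v < b is also below L, so the cell is low-to-low however far v falls. With an illustrative neutrophil limit of 1.5:

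- 1.2 to 0.05: low to low, no shift.
- 1.6 to 1.4: normal to low, a shift.

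**Step 2: timing.** Protocol Table 1 schedules hematology and chemistry after baseline on Days 7, 28, 56 and 84 or EOT, and SAP 6.5.2 reports on those days. The gaps are 28 − 7 = 21, 56 − 28 = 28 and 84 − 56 = 28 days. For mucormycosis, Protocol Table 2 adds Days 115, 145 and 180: 115 − 84 = 31, 145 − 115 = 30 and 180 − 145 = 35 days. SAP Appendix 1 allots Days 5–9, 26–30, 54–58 and, for aspergillosis, 77–91 to the first four visits. That leaves Days 10–25 (16 days), 31–53 (23 days) and 59–76 (18 days) outside any of the laboratory reporting days in SAP 6.5.2. Within a window, only the value closest to the target day is kept.

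**Step 3: what the other displays give.**

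| Display | What it shows | What it does not show |
|---|---|---|
| By-visit statistics (SAP 6.5.2) | Mean, SD, median, minimum and maximum of value and of change, so the most extreme child at that visit | How many children worsened severely |
| Listings (Protocol synopsis, 7.5.2) | Individual values, flagged if out of range | Grade or count |
| Adverse events (Protocol 5.4.2, 5.5.1.1; SAP 6.5.1) | Changes judged clinically significant, at any time | Abnormalities put down to underlying disease, unless judged worse than expected |
| Liver table (SAP 6.5.3) | Highest ALT and bilirubin against graded limits | Any non-liver test; change from baseline |

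Adverse event severity is defined by effect on daily activities (Protocol 5.5.4), so it does not serve as a laboratory grade.

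**Step 4: size, under assumptions.** N = 30 (Protocol 7.1). Let p be the share entering below range for one analyte and q the share who then worsen severely. Both are assumed, and q is taken as independent of baseline. I use q = 20%, so 30 × 0.2 = 6 children are expected to worsen.

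- Children who can show no downward shift: 30p.
- Expected severe cases not shown: 6p.
- Chance that the table shows none of the severe cases: (1 − q(1 − p))^30.

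| p | No downward shift possible | Can show one | Severe cases not shown, of 6 | Chance none shown |
|---|---|---|---|---|
| 20% | 6 | 24 | 1.2 | 0.84^30 = 0.5% |
| 50% | 15 | 15 | 3.0 | 0.90^30 = 4.2% |
| 80% | 24 | 6 | 4.8 | 0.96^30 = 29.4% |
| 90% | 27 | 3 | 5.4 | 0.98^30 = 54.5% |

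A table by severity category could show all six, provided each fall crosses a category boundary. Its chance of showing none is 0.80^30 = 0.1%.

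**The case against.** The strongest reply is that this is a conventional descriptive display and that the plan has other ways to see a severe fall. Much of that stands.

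- A reader might infer that severe worsening would be invisible everywhere. It would not. The by-visit minimum change shows the largest fall at each scheduled visit and is not averaged away. Individual values are listed, clinically significant worsening can be reported as an adverse event, and a DSMB reviews safety throughout (Protocol 10.1).
- A reader might infer that liver deterioration is missed too, since entry is refused only at "Alanine transaminase (ALT) or aspartate transaminase (AST) ≥ 5 times the ULN", or at bilirubin of 3 times the limit or more. An ALT rising from just under 5 to 20 times the limit is indeed high-to-high in the shift table, but SAP 6.5.3 counts it as above 10 times. The liver enzyme signal named in Protocol 1.2 and 1.3 is therefore covered.
- A reader might infer that children are known to enter out of range. The documents give no such rate: neutropenia is one host factor among several, and the cited cohort is described with and/or.
- A reader might extend the population argument to creatinine or creatine kinase. The classification rule works the same way there, but nothing in the documents suggests raised values at entry.

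What does not answer the point is the count. None of these displays says how many children worsened severely from their own baseline, and the adverse event exemption falls on cytopenias in particular. The minimum and maximum have a further difficulty: SAP 6.5.2 ties the quantitative summaries to a central laboratory, while Protocol 5.4.2 uses local laboratories, so the two must be reconciled. Table formats are deferred to separate TLF specifications (SAP 6.1), which are not part of these documents and should be checked.

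**Conclusion.** The point holds as a limited gap in a safety display. It is not an error or contradiction in the shift tables, and no efficacy analysis is affected. For any analyte outside the liver table, a child already out of range at entry cannot register further worsening in the same direction, and values between scheduled visits are not tabulated. The classification result follows from the text and needs no assumption.

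The size does rest on an assumption. If 50% to 90% of 30 children enter below range for a given blood count, 15 to 27 could show no downward shift; at 20% it would be 6. The case is strongest for hematology and secondary for creatinine, electrolytes and creatine kinase. The change is worth making because it is cheap and extends the highest-value, graded-limit approach that the SAP already uses for the liver.

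**What to change.** In SAP 6.5.2:

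1. Name in advance one published toxicity grading scale. Where it has no grade for a test, use stated multiples of the local age-specific limit.
2. Add a table of baseline category against worst on-treatment category, primarily for hematology and also for creatinine, electrolytes and creatine kinase. Use all results recorded in the eCRF, scheduled or unscheduled. Where both low and high values matter, tabulate each direction separately.
3. Count the children who worsen by at least one and by at least two categories.
4. Keep the low/normal/high by-visit table as supplementary, and point Protocol 7.5.2 to the new table.

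The cost is SAP wording and one programmed table, with no extra blood. There are two drawbacks. Falls due to chemotherapy or underlying disease will also appear, so the underlying disease needs noting beside the table. Values between visits will be included only where sites entered them: Protocol 5.4.2 requires recording of the protocol-specified tests and does not clearly require every interim local result.

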7.5.3 Vital Signs

Descriptive statistics will be used to summarize vital sign results and changes from baseline for subjects in the SAF by treatment visit.

Vital signs data will be displayed in listings.

7.5.4 Physical Examination

Physical examination will be listed.

7.5.5 Routine 12-lead Electrocardiograms

All 12-lead ECG results will be summarized by time point.

7.6 Analysis of Pharmacokinetics

Descriptive statistics (e.g., n, mean, standard deviation, minimum, median, maximum, coefficient of variation [CV], geometric mean and geometric CV) will be provided for plasma concentrations of isavuconazole.

7.6.1 Analytical Method

Isavuconazole plasma concentration will be determined by a validated LC-MS/MS method with a lower limit of quantitation (LLOQ) of 100 ng/mL.

7.6.2 Estimation of Pharmacokinetic Parameters

Plasma trough levels will be measured (pre-dose) on days 7, 14, 21, 42 and 84 or EOT.

24-hour pharmacokinetic samples will be measured on any day between days 14 and 42, while the subject is still receiving intravenous or oral study drug, for subjects who consent to participation in the 24-hour pharmacokinetic assessment.

Plasma concentrations will be analyzed using population pharmacokinetic model.

Population pharmacokinetics and/or pharmacokinetic/pharmacodynamics analyses will be performed by modeling and simulation scientist. All details of the population pharmacokinetic analysis will be described in a separate analysis plan and a separate population pharmacokinetic modeling report will be written.

7.7 Major Protocol Deviations and Other Analyses

Major protocol deviations as defined in [Section 8.3 Major Protocol Deviations] will be summarized for all enrolled subjects by site. A data listing will be provided by site and subject.

The major protocol deviation criteria will be uniquely identified in the summary table and listing.

7.8 Interim Analysis (and Early Discontinuation of the Clinical Study)

No formal interim analysis is planned.

7.9 Handling of Missing Data, Outliers, Visit Windows and Other Information

As a general principle, no imputation of missing data will be done. Exceptions are the start and stop dates of AEs and concomitant medication. The imputed dates will be used to allocate the concomitant medication and AEs to a treatment group, in addition to determining whether an AE is/is not treatment emergent. Listings of the AEs and concomitant medications will present the actual partial dates; imputed dates will not be shown.

See the SAP for details of the definition for windows to be used for analyses by visit.

Plasma concentration values below the LLOQ will be set to 0 for calculation of summary statistics. If one or more values are less than the LLOQ, the geometric mean will not be calculated.

